**Study hypothesis:****▪ Null hypothesis:**

No difference between the effectiveness of online oral health education and conventional oral health education methods on oral health knowledge and oral hygiene practice of primary school children

**4. Methods:**

- **Study design:** Randomized controlled trial (RCT)
- **Study settings:** 2 schools will be chosen (Al Rehab city and Al-Sherook city). The rationale behind choosing those two schools is to increase the sample size. Classrooms of grade three and grade four stages inside each school will be divided blindly into two groups; one receives the online oral health education while the other receives the conventional oral health education. Both schools had received simplified conventional oral health education service two years ago. The participants were of 5-6 years of age by then.
- **Study population:** Grade three and grade four Egyptian students aged 7-9 years old situated in 2 different schools related to Futures Educational Systems in Egypt.

Inclusion criteria	Exclusion criteria

 
• 2nd and 3rd grade Egyptian students.
 
• Average of age 7-9 years old.
 
• Currently residing in Egypt.
 
• Both male and female students.
 
	
 
• Those who do not consent to participate in the study.
 
• Those who cannot speak English or Arabic.
 
• Non-Egyptians.
 

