**NCT number: NCT05570500**

**Date of document: November 21st, 2020**

## **1. Background:**

Caries is one of the greatest challenges facing the health system in Egypt, and as of the past few years studies have shown that Egyptian children have many dental problems, including: untreated dental caries, forms of periodontal diseases and even irregular tooth brushing habits. The latter being mainly due to the ignorance of children of understanding the correct technique of tooth brushing, which may have been due to the lack of dental awareness that these children receive, either by dental professionals who should offer this service regularly [1] or due to poor parental awareness of the factors that affect the oral health status of their children [2].

Oral health (OH) education has proven to play a significant role in improving the knowledge, attitude and behaviour of children [3]. Implementing Oral health education in schools tend to improve the children's OH-related quality of life because engaging children at younger age regarding their habits, practices or knowledge tends to stay with them till adolescence then to adulthood [4].

In the year 2019 the Covid crisis has globally struck, being recognised by the WHO as a pandemic on March 11th, 2020 [5] the world was set in motion for various changes in the daily life of every man, woman and child. Covid 19, as defined by the WHO, is an infectious disease that spreads through droplets of saliva or discharge from the nose when the infected person sneezes or coughs, and thus the best way to avoid being infected by this disease is through some precautions that include social distancing of at least 1-2 meters between each person [6]. In Egypt, 75% of school children are usually very crowded in classrooms, which sometimes might reach 40 students per classroom or even more in certain schools [7]. Such numbers pose a great challenge to fulfilling the Covid precautions set by the WHO.

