**Framing the research question - PICOTS:**

P (participants): Primary school children of ages 7-9 years old in Egypt.

I (intervention): Online oral health education.

C (comparator): Conventional oral health education.

O (primary outcome): Improving the oral hygiene knowledge and practice in primary school children.

T (Time of follow up): Every 3 months interval for one academic year.

S (Study settings): 2 schools will be chosen (Al Rehab city and Al-Sherook city). The rationale behind choosing those two schools is to increase the sample size. Classrooms of grade two and grade three stages inside each school will be divided blindly into two groups; one receives the online oral health education while the other receives the conventional oral health education. Both schools had received simplified conventional oral health education service two years ago. The participants were of 5-6 years of age by then.

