**Recruitment:**

Recruitment will start in September 2022 through sending the children's parents papers of consent via their channel books during the school day.

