### **Study procedures:**

- 1) A literature review was conducted using electronic search engines like PubMed and Google scholar to identify studies assessing the effect of online and conventional oral health education on improving the oral health knowledge and practice in school children regarding their oral hygiene.
- 2) After reviewing many articles, a questionnaire was selected to assess the above outcomes. The questionnaire was chosen according to availability and effectiveness, and it was modified by simplifying and deselecting some of the questions that aren't related to the age group to better suit the age group of question.
- 3) A piloting session will be done on two separate classes, one from each educational stage to assess the modified questionnaire in terms of ease of understanding and comprehension to the participants. Those two classes will not be included in the final results of the study.
- 4) The questionnaire will be distributed before conducting the oral health education sessions (both online and conventional) to assess the pre-session knowledge and practice of the participants.
- 5) All questionnaires are self-administered but a well-trained interviewer will be available offering assistance in understanding the questionnaires if needed.
- 6) 3rd and 4th grade classrooms in each school will be randomly and evenly allocated to the interventions included in the study using computer-generated randomization application.
- 7) The researcher will be blinded of the classrooms of each school during the randomization process.
- 8) The researcher will be blinded of the names of the participants or their personal data during and after the questionnaire session.
- 9) After the questionnaire is finished, the researcher will then begin his educational lesson using electronic aids like a projector inside the classrooms or using Microsoft teams during the online session.
- 10) Another questionnaire will be distributed after the educational lesson for both session types to assess the post-session knowledge and practice in the participants.
- 11) A comparison will be carried out for the results of each question in both questionnaires and for the final results of both questionnaires to determine the statistical significance of both results.
- 12) These statistical results will be done by a separate statistician outside the study field and blinded from all the procedures.

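### Classrooms are allocated evenly within school but balance by grade is not stated, although age and possibly earlier conventional teaching follow grade, and the account of that teaching does not clearly cover ages 7-9

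*Protocol*

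**What the plan says.** **Allocation.** Study procedures, step 6, says of the third- and fourth-year classes: "grade classrooms in each school will be randomly and evenly allocated to the interventions included in the study". School is named as the level at which the split is even. Grade is not.

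**Earlier teaching.** Section 4 (Study settings) and the PICOTS framing carry the same statement: "Both schools had received simplified conventional oral health education service two years ago. The participants were of 5-6 years of age by then". The earlier service was of the conventional type, which is the comparator in this trial.

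**Population.** Section 4 describes "Grade three and grade four Egyptian students aged 7-9 years old situated in 2 different schools". Its Study settings item agrees on the grades: "Classrooms of grade three and grade four stages inside each school will be divided blindly into two groups". The PICOTS framing differs: "Classrooms of grade two and grade three stages inside each school will be divided blindly into two groups". The inclusion criteria also give 2nd and 3rd grade.

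**Dates.** The front matter reads "Date of document: November 21st, 2020". The Recruitment section reads "Recruitment will start in September 2022". The chart in section 7 places data collection and entry in January to August 2021.

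**Baseline.** Step 4 gives every child a questionnaire before the teaching, "to assess the pre-session knowledge and practice of the participants".

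**The concern.** Whole classrooms are randomised, so the number of independent units is small. An even split within each school guarantees balance by school. Unless grade is also controlled, it leaves to chance how many older-grade classes each arm receives.

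That matters because grade carries several things that bear on a knowledge and practice score: age, the ability to read a self-administered questionnaire, and possibly whether and how long ago a child met the conventional programme. Earlier teaching may raise the starting score and leave less room to gain. If one arm drew more older-grade classes, the online-versus-conventional difference would partly reflect those features.

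The protocol presents the earlier teaching as common to all participants at age 5-6. If that held for the whole eligible range, the exposure part of the concern would be smaller. It does not clearly hold, and the conflicting dates and grades prevent a reader from working out which children were covered.

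**Working it through.** **1. The planned number of children.** The Sample size calculation gives 265 per intervention. A two-sided paired t-test with d = 0.2, alpha = 0.05 and 90% power reproduces this (n = 265, power 0.9004). Then 265 × 1.2 = 318, and 2 × 318 = 636. The figure is used here only to gauge how many classrooms might be involved.

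**2. Do children aged 7-9 match an age of 5-6 two years ago?** Read both ranges in completed years (5.0-6.99 and 7.0-9.99). If two years ago is counted from the document date, the programme ran about 21 November 2018. Age at the study is age then plus the gap.

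| Study date | Gap (years) | Aged 5-6 then, now aged | Aged 7-9 now, then aged |
|---|---|---|---|
| Document date, November 2020 | 2.00 | 7.0-8.99 | 5.0-7.99 |
| Timeline, start of January 2021 | 2.11 | 7.1-9.1 | 4.9-7.9 |
| Timeline, end of August 2021 | 2.78 | 7.8-9.8 | 4.2-7.2 |
| Recruitment, September 2022 | 3.78 | 8.8-10.8 | 3.2-6.2 |

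If two years is counted back from enrolment instead, the first row applies whatever the calendar date. No row covers the full eligible range. The statement fits only if 7-9 means 7.0 to 9.0 and the gap is exactly two years: 7.0 − 2 = 5.0 and 9.0 − 2 = 7.0.

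**3. Chance imbalance by grade.** Assumptions: two schools of equal size, two grades with m classes each per school, and half of each school's 2m classes drawn for each arm without regard to grade. The number k of lower-grade classes in one arm in one school is hypergeometric:

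P(k) = C(m,k)² / C(2m,m)

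The two schools are independent, so the total K is the convolution of two such distributions. Each arm has 2m classes. The arms' shares of the lower grade therefore differ by |2K − 2m| / 2m.

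*Sixteen classrooms (m = 4; 636/40 = 15.9).* The class size of 40 is a background remark in section 1 about some Egyptian schools, not a figure for these two.
- Per school, k = 0 to 4 has weights 1, 16, 36, 16, 1 out of 70.
- Exact balance over both schools (4-4): (1 + 256 + 1296 + 256 + 1)/4900 = 1810/4900 = 0.369.
- A difference of at least 25 points (5-3 or worse): 1 − 0.369 = 0.631.
- A 5-3 split: 2 × 1184/4900 = 0.483. A difference of at least 50 points (6-2 or worse): 722/4900 = 0.147.

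*Twenty-four classrooms (m = 6; 636/24 = 26.5 children per class).*
- Per school, k = 0 to 6 has weights 1, 36, 225, 400, 225, 36, 1 out of 924.
- Exact balance (6-6): 263844/853776 = 0.309.
- A 7-5 split, a difference of 2/12 or about 17 points: 392544/853776 = 0.460.
- At least 25 points (8-4 or worse): 197388/853776 = 0.231. At least 50 points (9-3 or worse): 0.044.

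Part of the fall from 0.63 to 0.23 arises because a one-class departure is exactly 25 points with 16 classrooms but only 17 points with 24. The chance of some imbalance is 0.63 and 0.69 respectively. What more classrooms reduce is large imbalance.

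**The case against.** A reader might infer that carry-over from the earlier programme biases the comparison. The documents do not support that. Allocation is random, so grade and earlier exposure are balanced in expectation, and what remains is chance imbalance. The protocol describes the earlier service as given to both schools. It does not say that it was confined to children aged 5-6 or name any grade left out. Exposure at school level is balanced by the within-school split. That differential exposure follows grade is therefore a possibility, not a stated fact.

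A reader might also infer that only about 40% of the eligible age span was old enough to have been taught: (6.21 − 5)/(9.99 − 7) = 0.40. That combines the November 2020 anchor with September 2022 recruitment and ignores the Timeline, under which most of the range fits. It is one outcome of a date conflict, not an estimate of exposure.

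Further points stand in the protocol's favour. Baseline is measured in every child, so a difference in starting level would be visible, although a questionnaire score cannot separate age from earlier teaching. Covariate adjustment may be set out in an analysis plan that is not at hand, so its absence here is not a fault. Step 6 can be read as splitting both grades evenly. The classroom count is assumed, and the probabilities concern grade mix; nothing in the documents converts them into an effect on the outcome.

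Two things survive. Balance by grade is not explicit in the section that fixes the randomisation. The age statement and the dates and grades it depends on do not agree.

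**Conclusion.** The point holds as a low-to-moderate design weakness with a documentation inconsistency attached. Step 6 secures balance by school and leaves balance by grade unstated. If grade is in fact uncontrolled, a difference of at least 25 percentage points in the arms' grade mix has probability about 0.63 with 16 classrooms and 0.23 with 24; for at least 50 points the figures are 0.15 and 0.04. These rest on equal grades and schools and on an assumed number of classrooms.

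Separately, the claim that participants were aged 5-6 two years ago does not clearly cover ages 7-9. It fits fully only on a narrow reading of the age range at exactly two years. Which ages fit otherwise depends on dates that conflict within the protocol, and the eligible grades conflict as well.

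**What to change.** - **Randomisation (step 6).** Run the computer allocation separately within each school-by-grade block, after the pilot classes have been set aside. This takes one line and no extra children, but it must be done before allocation. An odd number of classes in a grade leaves one class of unavoidable imbalance.
- **Between-arm comparison.** Include grade and baseline score. This uses data already collected.
- **Reconcile the text.** State when the earlier programme ran and which grades received it. Bring the eligible grades into agreement across the PICOTS framing, section 4 (settings, population and inclusion criteria) and step 6. Align the Recruitment date with the section 7 Timeline and the document date.
- **Earlier exposure.** Record it at grade or classroom level, and only where school records allow this without identifying children. Marking individual children from old records would sit badly with step 8, which blinds the researcher to names and personal data, and with the anonymity promised under Ethical consideration. Present classes may also not match the earlier ones, so this record may be incomplete.

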**Sampling:****Type of sample:**

A convenient sample will be recruited to participate in the study.

**Recruitment:**

Recruitment will start in September 2022 through sending the children's parents papers of consent via their channel books during the school day.

### **Sample size calculation:**

Sample size estimation was based on testing the change in KAP before and after each educational intervention. The predicted sample size was found to be 265 children for each intervention, by assuming an  $\alpha$  level of 0.05,  $\beta$  level of 0.1 (power = 90%), allocation ratio of 1:1, to detect an effect size  $d$  of 0.2. After adding a 20% increase to adjust for dropout, the final sample size was 318 children for each intervention (total sample size = 636 children). Sample size calculation was performed using G\*Power software version 3.1.9.4 for MS Windows, Franz Faul, Kiel University, Germany.

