**3. Aim:**

The aim of this study is to compare the results of the comparison between the online oral health education and conventional oral health education methods in terms of their effectiveness towards improving the knowledge and practice of oral hygiene in primary school children in Egypt.

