**Objectives:**

➤ **Primary objective :**

- To compare the online oral health education to the conventional oral health education regarding :
  1. Oral health knowledge of primary school children of 7-9 years old.
  2. Assessing oral hygiene measures practice in primary school children of 7-9 years old.

➤ **Secondary objective :**

Is to evaluate the efficacy of a new oral health education method to deliver health information to target population

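### The 265 children per arm and 90% power are for a before-to-after test within one arm; no power is stated for the primary online-versus-conventional comparison

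*Protocol*

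**What the plan says.** The section Sample size calculation names the test it sizes: "Sample size estimation was based on testing the change in KAP before and after each educational intervention". Its inputs are alpha 0.05, 90% power, d = 0.2 and equal allocation, and its result is "The predicted sample size was found to be 265 children for each intervention". A 20% increase for dropout brings this to 318 per arm and 636 in total.

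The question the trial sets out to answer is stated elsewhere and is between arms. Section 3 (Aim) is to "compare the results of the comparison between the online oral health education and conventional oral health education methods". The primary objective is "To compare the online oral health education to the conventional oral health education regarding" two things, listed separately: "Oral health knowledge of primary school children of 7-9 years old" and "Assessing oral hygiene measures practice in primary school children of 7-9 years old". The null hypothesis is that the two methods do not differ in effectiveness. Section 2 words the research question as one of equal effectiveness, without a margin.

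The protocol gives no power, detectable difference or assumed effect for online versus conventional.

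**The concern.** A before-to-after test asks whether children in one arm improve. The null hypothesis asks whether the arms differ. These are separate questions: both arms could improve by 0.2 SD, each within-arm test could be significant, and the null hypothesis of no difference would still be true.

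The 90% is the only power figure in the protocol, so a reader will naturally attach it to the primary comparison. The risk is greatest for a non-significant result. Because the research question asks whether online teaching matches conventional teaching, such a result could be read as favourable and credited with 90% power that was never calculated for it.

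**Working it through.** **Inputs from the protocol (Sample size calculation):** alpha 0.05 (sidedness not stated), power 90%, d = 0.2, 265 per arm, 318 per arm after the dropout increase. No SD, pre-post correlation, class size or intraclass correlation (ICC) is given.

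**Step 1. Which test gives 265?** Power comes from the noncentral t distribution. The noncentrality is d × √n for a paired test (n − 1 degrees of freedom) and d × √(n/2) for two groups of n (2n − 2 degrees of freedom).

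| Test at d = 0.2, 90% power | n required |
|---|---|
| Paired, two-sided | 265 (0.9004; 264 gives 0.8993) |
| Paired, one-sided | 216 |
| Two-group, one-sided | 429 per arm |
| Two-group, two-sided | 527 per arm (0.9004; 526 gives 0.8998) |

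Of these four, only the two-sided paired test gives 265. As a check, the normal approximation is ((1.960 + 1.282)/0.2)² ≈ 262.7, slightly below the t-based figure as expected. The dropout step also reproduces: 265 × 1.2 = 318. So the wording and the arithmetic both point to a within-arm test with d in units of the SD of change and children treated as independent.

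**Step 2. What do these numbers give for the between-arm comparison?** The protocol states no between-arm effect, so a range is shown. The table is for a two-sided two-group t-test on change scores with independent children.

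| Assumed difference (SD of change) | Power, 265 per arm | Power, 318 per arm |
|---|---|---|
| 0.10 | 21% | 24% |
| 0.15 | 41% | 47% |
| 0.20 | 63% | 71% |
| 0.25 | 82% | 88% |
| 0.30 | 93% | 97% |

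For example, 265 per arm at 0.20 gives noncentrality 0.2 × √(265/2) = 2.30 and power 0.632. Power of 90% is reached at 0.282 SD (265) or 0.257 SD (318).

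**Step 3. Sensitivity to baseline adjustment.** With equal pre and post SDs and correlation r, adjusting for baseline turns 0.2 SD of change into an effective d of 0.2 × √(2/(1 + r)). With 265 per arm, power is 81%, 76% and 70% at assumed r = 0.3, 0.5 and 0.7. If 0.2 is instead in raw-score SD units, the effective d is 0.2/√(1 − r²), and power is 63%, 76% and 94% at assumed r = 0, 0.5 and 0.75.

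**Step 4. Sensitivity to clustering.** Study procedures item 6 allocates classrooms. Take a design effect of 1 + (m − 1) × ICC and an effective n of 265 divided by it. The class size m and the ICC are both assumptions, and the ICC that matters is that of the analysed score.

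| Assumed m, ICC | Design effect | Effective n per arm | Within-arm power at 0.2 | Between-arm power at 0.2 |
|---|---|---|---|---|
| none | 1 | 265 | 90% | 63% |
| 25, 0.01 | 1.24 | 213.7 | 83% | 54% |
| 40, 0.05 | 2.95 | 89.8 | 47% | 27% |

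The between-arm difference detectable with 90% power becomes 0.31 and 0.49 SD in the two clustered cases.

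**The case against.** The best reply is that the protocol hides nothing. The sample size section names its test, and within-arm improvement has a real place in the document: the PICOTS outcome is worded as improvement, the secondary objective concerns the efficacy of the new method, and Study procedures item 11 compares the two questionnaires. All of that stands. It makes the before-to-after test a legitimate analysis, but not the test of the primary objective or the null hypothesis.

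A second reply is that 265 could be right for a between-arm test. If d = 0.2 were in raw-score SD units and the pre-post correlation were 0.75, the SD of change would be √(2 × 0.25) = 0.707, the effective d would be 0.2/0.707 = 0.283, and 264 per arm would suffice (265 gives 0.901). The arithmetic is correct, but the protocol states neither that scale nor that correlation, and its text describes a before-to-after test. What does stand is that the paired, two-sided, SD-of-change reading is inferred from one sentence and an exact numerical match, so the sponsor should confirm it. It also stands that between-arm power cannot be determined from the protocol: 63% is an illustration, not an estimate.

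Thirdly, clustering is a separate matter, and the argument does not need it. The clustered figures show only that any positive within-class correlation lowers both tests. The equal-allocation phrase, "allocation ratio of 1:1, to detect an effect size" and so on, is minor: it may simply describe arms of equal size, and it is not an input to a paired test.

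**Conclusion.** The concern holds and must be fixed. The 265 per arm and 90% power belong to a within-arm before-to-after change of 0.2 SD of change, whereas the aim, primary objective and null hypothesis are between arms. The 90% cannot be quoted for online versus conventional.

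This does not show that the trial is underpowered. With 265 per arm and independent children, between-arm power runs from 21% to 93% as the assumed difference goes from 0.10 to 0.30 SD of change. Where the trial falls in that range depends on an effect the protocol does not state, and then on the gain from baseline adjustment and the loss from clustering.

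**What to change.** Rewrite the Sample size calculation paragraph as follows.

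1. State that 265 and 90% apply only to the within-arm before-to-after change. Confirm that the test is two-sided, that d = 0.2 is in units of the SD of change and that children were treated as independent. Say that 1:1 describes equal arms.
2. For the between-arm test of the null hypothesis, state the power, or the difference detectable with 90% power, at the planned number. Name the outcome (knowledge, practice or total KAP score) and the time point, since PICOTS plans three-monthly follow-up and Study procedures item 10 a post-lesson questionnaire. Give the assumed effect with its scale, the analysis assumed, and a classroom design effect with its class size and ICC.
3. Do not attach the 90% to the online-versus-conventional comparison, or to the equal-effectiveness wording of section 2, which has no margin.

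The cost is one paragraph and one recalculation. The correction itself does not change enrolment. The downside is that the stated power for the primary comparison may turn out below 90%; if so, the sponsor should see that before recruitment rather than after the result.

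### The sample size rests on one undefined KAP change, while the primary outcomes are knowledge and practice, and no result is named as deciding the trial

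*Protocol*

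**What the plan says.** The protocol describes its endpoint in three ways.

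- **Sizing endpoint.** Under Sample size calculation: "Sample size estimation was based on testing the change in KAP before and after each educational intervention". The inputs are alpha 0.05, power 90%, 1:1 allocation and one standardised effect of d = 0.2, and "The predicted sample size was found to be 265 children for each intervention". Adding 20% for dropout gives 318 per arm and 636 in total. KAP is not spelled out, and d has no scale, standard deviation or source.
- **Primary outcomes.** The PICOTS frame gives the primary outcome as "Improving the oral hygiene knowledge and practice in primary school children". The primary objective compares the two methods on two numbered items: oral health knowledge, and "Assessing oral hygiene measures practice in primary school children of 7-9 years old". The aim and the null hypothesis name the same two domains, and both compare online with conventional education. Steps 4 and 10 of Study procedures say that the pre-session and post-session questionnaires assess knowledge and practice.
- **Planned comparisons.** Step 11 of Study procedures says "A comparison will be carried out for the results of each question in both questionnaires and for the final results of both questionnaires", with the purpose of determining statistical significance.

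Attitude appears only in the Background, as something oral health education can improve, and in the title of a cited study (reference 11), where knowledge, attitude and practice stand together.

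**The concern.** The endpoint that justifies the number of children should be the one on which the trial is judged. Here the sizing quantity is a single change under a label that the objectives do not use, the objectives name two outcomes, and the planned comparisons name neither a knowledge score nor a practice score. Nothing marks one result as decisive.

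Two things are at stake.

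1. **What can be claimed.** A single lesson may raise knowledge answers while practice answers stay the same. If the final result is a total score, it could reach significance on the knowledge items alone and still be reported as a gain in knowledge and practice. Testing every question adds further routes to an isolated significant finding.
2. **What the power statement means.** A reader will take the 90% to apply to the primary objective. It was calculated for one before-after change within each arm.

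**Working it through.** **Inputs.** From Sample size calculation: alpha 0.05 (sidedness not stated), power 0.90, d = 0.2, 265 per arm before dropout and 318 after. From Objectives and Study hypothesis: two outcomes, compared between arms.

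**Step 1: reproduce 265.** For a paired t-test the noncentrality is d√n. The smallest n with two-sided alpha 0.05 and power at least 0.90 at d = 0.2 is 265, with power 0.9004. The normal approximation, ((1.960 + 1.282)/0.2)², gives 263. Other readings do not give 265: one-sided paired needs 216, two independent means need 527 (two-sided) or 429 (one-sided). The dropout step is 265 × 1.2 = 318. The plan's figure is therefore a two-sided, within-arm, before-after calculation for one change score.

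**Step 2: does the label matter to n?** The calculation uses d alone. Any single change score with d = 0.2 needs the same 265 at 90% power, whether it is called KAP, knowledge or practice. Removing attitude changes nothing unless a different d applies, and the protocol gives none.

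**Step 3: power for the stated objective.** Assume that d = 0.2 is the between-arm difference in standard deviations of the score compared, for each outcome. The noncentrality is then d√(n/2).

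| Children analysed per arm | d√(n/2) | Power, one outcome | Power, both outcomes if independent |
|---|---|---|---|
| 265 | 0.2 × √132.5 = 2.30 | 0.632 | 0.632² = 0.40 |
| 318 (no dropout) | 0.2 × √159 = 2.52 | 0.712 | 0.712² = 0.51 |

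If the outcomes were perfectly correlated, power for both would equal power for one. For 90% on one outcome, 527 per arm are needed; with 265 per arm, 90% power is reached at a difference of about d = 0.28. If alpha were split instead (0.025 each), power per outcome at 265 per arm would be 0.522, and 622 per arm would be needed for 90%. None of these figures allows for the allocation of whole classrooms, which would lower power further if children within a classroom are alike.

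**Step 4: question-level testing.** With k independent tests at 0.05, the chance of at least one false positive is 1 − 0.95^k: 0.401 for k = 10 and 0.642 for k = 20. The protocol does not give the number of questions, so 10 to 20 is an assumption. Items on one questionnaire are likely to be correlated, which would give lower figures.

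**The case against.** The strongest reply is that this is a matter of wording. KAP is undefined, may be loose shorthand for the questionnaire's overall score, and has no effect on the number: 265 follows from d = 0.2 under any label. That stands. A reader might infer that the 90% power belongs to an endpoint the trial does not have, or that attitude is not measured. The documents support neither. The questionnaire's items are not shown, so all that can be said is that attitude is not a named outcome.

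A second reply is that the protocol never says knowledge and practice are summed. Step 11 speaks of the final results of both questionnaires, which fits the pre-session and post-session forms. That also stands, so the risk from a pooled total is conditional on there being one.

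A third reply is that multiplicity rules commonly belong in a statistical analysis plan, which is not at hand, and that no section says success on any single question will be claimed. This is fair, and the error rates in step 4 are illustrations only. It does not remove the point. The identity of the primary endpoint and its match to the sizing endpoint are protocol content, and here the sections disagree. Step 11 also commits to comparing every question for significance.

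A further tempting reading is that joint power for the two outcomes is 0.90² = 0.81 at worst and 0.90 at best. That range starts from the within-arm 90% and does not describe the between-arm objective, where the figures are lower.

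**Conclusion.** The inconsistency is certain: the trial is sized on one undefined KAP change, its primary outcomes are knowledge and practice, and its planned comparisons are every question plus the final results, with none marked as decisive. The label by itself costs no power.

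The stated 90% holds only for one within-arm before-after test at d = 0.2. For the between-arm objective it is about 63% per outcome at 265 per arm and 71% at 318, or about 40% and 51% for both outcomes. Those figures assume that 0.2 is the between-arm difference for each outcome and, for the joint figures, that the outcomes are independent; they make no allowance for classroom allocation. The 40% to 64% question-level error rests on an assumed item count and on independence, and correlated items would give less. The point should be corrected before analysis because the correction is nearly free and limits what the trial could wrongly claim.

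**What to change.** - **Sample size calculation:** replace KAP with the knowledge score and the practice score of the primary objective, and give d and its basis for each.
- **Objectives and outcome:** score and report knowledge and practice separately as the primary outcomes. Claim benefit on both only if both are supported, or state another multiplicity rule.
- **Study procedures, step 11:** make the question-by-question comparison and any total score descriptive.
- **Power statement:** say that the present 90% applies to a single within-arm change at d = 0.2. Then give the power of the between-arm comparison for each outcome, and for both together under the chosen rule, with an allowance for classroom allocation. Do not print 81% to 90%.

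**Cost:** protocol wording and two sub-scores from the same form, with no extra data collection. The downside is a less favourable stated power, and the sponsor would have to accept that openly or revisit the sample size.
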